#### 6.1.3 Secondary Effectiveness Endpoints:

- Number of subjects reporting >5% total body weight loss at the end of Therapy as compared to Baseline between Treatment and Control
- Percent change in appetite scores at the end of Therapy Period compared to Baseline between Treatment and Control.
- Blood pressure, blood lipids, ALT and HbA1c at the end of Therapy Period as compared to Baseline between Treatment and Control groups.
- % changes in BMI at the end of Therapy Period compared to Baseline between Treatment and Control groups

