## **PROTOCOL SUMMARY**

Study Title	Safety and effectiveness of transcutaneous electrical nerve stimulation (TENS) of the T6/T7 dermatome in adult, overweight-to-Type 1 obese- subjects (i.e. BMI of between 25 to 35 kg/m² inclusive) when used for weight loss.
Study Coordinating Pls	[name] and [name]
Study Rationale	Previous studies have shown that TENS facilitates weight loss in overweight subjects. The therapy in these trials was delivered using an over the counter device not optimized for daily use for weight loss.
	The present pivotal study will test the hypothesis that daily, wearable TENS is safe and effective for weight loss therapy in overweight- to Type 1 obese-subjects (i.e. BMI of 25 -35 kg/m² inclusive). Secondarily the study will assess the impact of the TENS therapy on appetite. Ancillary endpoints include changes in hemoglobin A1c, changes in ALT, and blood lipids as secondary measures associated with weight loss.
Name of the Device(s) Used in Study	The Elira wearable, patch system.
Description of Components	The Elira wearable patch system is an RF coupled, wearable transcutaneous electrical nerve stimulation (TENS) device controlled via Bluetooth by a smart phone unit running a custom application which directs therapy from the patch within safe limits set by a clinician and also includes a diary. Subjects will be supplied as well with paper diaries for appetite and symptoms along with an electronic scale.
Study Design	Randomized, adaptive parallel arm study. Subjects will be initially screened during a screening period (+/- 7 days). During this screening period, subjects will sign an Informed Consent Form (ICF), have their weight/height and blood pressure measured, take a pregnancy test (females of child bearing potential), get blood drawn for analysis (CMP, blood lipids, hemoglobin A1c), and complete the PHQ-9 and patient preference survey.
	At the end of the screening period, eligible subjects will be enrolled/randomized in the study to either a treatment or control group. After enrolling, both control and treatment subjects will be instructed to follow a healthy 1200 calorie diet for the duration of the study and will receive training on the use of the electronic scale and completion of paper diaries. For the treatment group, subjects will be instructed on use of the Elira wearable, patch system. Following this, subjects will enter the Therapy Period for 12-weeks.

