#### 2.1 JUSTIFICATION FOR STUDY GIVEN RISK/BENEFIT OUTCOME

Up to 35% of adults over the age of 20 in the United States are overweight. Being overweight places individuals at higher risk for a number of what are termed metabolic disorders including diabetes mellitus. This risk association is thought to be the reason for the high health care costs associated with overweight and obesity. While diet and exercise do show efficacy in a substantial subset of subjects, long term weight control is difficult to achieve for the vast majority of overweight individuals. The physiological and psycho-social reasons for this are not well characterized and likely highly complex, but a key component of this challenge is associated with appetite control. The present study seeks to determine if a method of appetite control utilizing T6/T7 dermatome stimulation in obese individuals can be utilized to the broader overweight population. The study utilizes non-invasive TENS stimulation within the range of the energy delivery well known to be safe for at-home use for nerve and muscle pain. Subjects will be informed of all potential side effects related to stimulation prior to enrollment and, throughout the study, subjects will be monitored and allowed to decrease or discontinue stimulus if any such side effects are deemed to be intolerable for participants.

In addition, since appetite and weight loss can be affected by a variety of physiological and psychosocial factors (12,13, 15, 17), the change in appetite will be measured weekly using a validated tool, the Visual Analog Scale (VAS; See Appendix 3) and also assessed at baseline at the end of the study via administration of the Three Factor Eating Questionnaire R-18 V2 (TFEQ-R1V2). Please note that while the VAS was first developed for pain, it has been validated for weight loss/appetite applications (14) while the TFEQ-R18V2 has specifically been validated in weight loss applications (17, 18). The present study is not intended to be a formal validation of the assessment tool's applicability to the population targeted by the present study per se; it is intended simply as an assessment of potential changes in such parameters correlated with delivery of therapy during the study. Thus, the use of the tool as presented is considered scientifically valid.

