#### 8.1.2 Appetite Suppression

The null and alternative hypotheses are:

$$H_0$$
:  $π_T ≤ π_C$ 
 $H_1$ :  $π_T > π_C$ 

Where  $\pi_T$  and  $\pi_C$  are the probabilities of appetite suppression in treatment versus control respectively. Pearson correlation will be utilized to correlate appetite score (as measured with TFEQ-18V2; ) with stimulation dose. Estimates of 95% confidence intervals will also be computed for the difference between varying levels of stimulation. Wilcoxon signed rank tests and/or Kruskal Wallis statistics will be utilized to make comparisons between groups as required. Estimates and 95% confidence intervals will also be computed for the difference in appetite levels between Baseline and Therapy Periods.

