#### 9.8 QUESTIONNAIRES

All subjects will be required to complete the Patient Preference Survey and PHQ-9 at screening/baseline visit. All subjects will be required to complete a weekly VAS diary for hunger and appetite from screening/baseline until completion of the study. All subjects will be required to complete the TFEQ-R18V2 at enrollment and at each Therapy Visit (Appendix 3). All subjects will be required to complete PHQ-9, TFEQ-R18V2, and Patient Preference Survey at the last study visit (Visit 5 or early termination visit).

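### The appetite endpoint rests on one end-of-therapy reading with last value carried forward, no between-arm analysis of the weekly VAS series is specified, and the documents do not settle which instrument supplies the score

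*Combined protocol and SAP*

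**What the plan says.** The Protocol Summary gives appetite as the secondary aim: "Secondarily the study will assess the impact of the TENS therapy on appetite". The endpoint in Section 6.1.3, repeated in the Summary, is "Percent change in appetite scores at the end of Therapy Period compared to Baseline between Treatment and Control".

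Two instruments collect appetite data.

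- **Weekly VAS.** Section 9.8: "All subjects will be required to complete a weekly VAS diary for hunger and appetite from screening/baseline until completion of the study". Section 5.2 asks the same of all subjects. Section 2.1 presents this as the measure of appetite change: "the change in appetite will be measured weekly using a validated tool, the Visual Analog Scale".
- **TFEQ-R18V2.** Section 9.8: "All subjects will be required to complete the TFEQ-R18V2 at enrollment and at each Therapy Visit". With the Visit 5 administration, that gives Week 0 and Weeks 1, 4, 8 and 12. Section 8.1.2 takes the score from this questionnaire: "Pearson correlation will be utilized to correlate appetite score (as measured with TFEQ-18V2".

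Section 6.2 refers to the appendices for both. Section 8.1.2 states its hypothesis in terms of the probability of appetite suppression and names rank tests for group comparisons. It adds: "Estimates and 95% confidence intervals will also be computed for the difference in appetite levels between Baseline and Therapy Periods". Section 8.3 imputes missing data by last value carried forward, after allowing a one-week look-back for missed diary entries. Section 8.2 assumes 30% dropout.

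**The concern.** If the VAS is the score, about 12 on-therapy readings per subject are collected in both arms and at most one enters the between-arm endpoint. If the TFEQ is the score, three of its four on-therapy readings stay outside the endpoint, and the weekly diary has no specified between-arm analysis at all.

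Three features add to this.

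- The diary form asks how the subject feels at one moment before a meal, so a single reading carries moment-to-moment noise.
- Carrying the last value forward lets an early reading stand as the end-of-therapy value for subjects who drop out. At the assumed rate that is 0.30 × 75 = 22.5, or about 22 to 23 subjects per arm.
- A percent change divides by the baseline score, which is unstable when a subject marks a VAS line near zero.

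Appetite suppression is the hypothesised mechanism (Section 1.3). An imprecise or distorted appetite result would weaken the explanation of any weight effect.

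**Working it through.** **Inputs.** The documents give no SD, effect size or within-subject correlation for appetite, and no appetite sample-size figure to reproduce. The 75 per group in Section 8.2 is for %TBWL and is used here only to obtain 75 × 0.7 = 52.5, taken as 52 completers per arm. The correlation r and the effect size are my assumptions. Variances are relative to one reading. The ratios are for absolute change; none was derived for percent change.

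**1. Change from baseline, equal correlation r between all readings.** The variance for a single reading is 2(1 − r). For a mean of k readings it is (1 + 1/k)(1 − r). The ratio is (1 + 1/k)/2, whatever r is.

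- k = 4: (1 + 0.25)/2 = 0.625
- k = 12: (1 + 0.0833)/2 = 0.542

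About 37% and 46% of the single-reading variance could thus be removed. The four TFEQ visits also give 0.625.

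**2. The on-therapy component alone.** The ratio is (1 + (k − 1)r)/k.

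| r | k = 4 | k = 12 |
|---|---|---|
| 0.3 | 0.475 | 0.358 |
| 0.5 | 0.625 | 0.542 |
| 0.7 | 0.775 | 0.725 |

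**3. Correlation that decays with distance, r^(weeks apart).** For change from baseline, the ratio for the mean of the last four weeks rises to 0.694, 0.757, 0.825, 0.846 and 0.847 at week-to-week r of 0.3, 0.5, 0.7, 0.8 and 0.9. The gain is then 31% down to 15%, not 37%.

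**4. Shape of the effect.** Assume r = 0.7 (equal correlation), baseline adjustment, 52 per arm, a Week 12 effect of 0.3 SD and two-sided 0.05. The standard error of the difference is √(variance × 2/52), and power is Φ(effect/SE − 1.96).

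| Estimate | Variance | Power, constant effect | Power, linear build-up |
|---|---|---|---|
| Week 12 only | 1 − 0.49 = 0.51 | 57% | 57% |
| Mean, Weeks 9-12 | 0.25 + 0.7 × 0.75 − 0.49 = 0.285 | 82% | 71% |
| Mean, Weeks 1-12 | 1/12 + 0.7 × 11/12 − 0.49 = 0.235 | 88% | 40% |

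Under linear build-up the mean effect is 0.3 × 0.875 = 0.2625 for Weeks 9-12 and 0.3 × 0.5417 = 0.1625 for Weeks 1-12. Under decaying correlation of about 0.8 or more with linear build-up, the advantage of the Weeks 9-12 mean disappears.

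**5. What a model gives for Week 12 itself.** With complete data and an arm-by-week term, a repeated-measures model returns essentially the baseline-adjusted Week 12 comparison. The gain over unadjusted change is then (1 − r²)/(2(1 − r)) = (1 + r)/2, which is 0.65, 0.75 and 0.85 at r = 0.3, 0.5 and 0.7. The intermediate readings help that contrast by informing it for subjects who drop out, in place of a carried-forward value. The ratios in step 1 apply to averages over weeks.

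**The case against.** The strongest reply is that Section 8.1.2, the only analysis section on appetite, takes the score from the TFEQ. That instrument has four on-therapy readings, asks largely about habitual eating and has a baseline scheduled for everyone at Visit 1. On that reading, arguments about a momentary scale and a thin baseline fall away, and a Weeks 9-12 mean would contain one scheduled reading. This stands as far as it goes, but Section 2.1 names the VAS and Section 6.2 points to both. The conflict is part of the problem.

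An end-of-therapy landmark also matches the timing of the primary endpoint and is a legitimate target. Replacing it with an average would change the question, and step 4 shows that a 12-week mean can cost power. This stands, and the landmark should be kept.

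Section 8.1.2 further plans a baseline-versus-therapy estimate, and Section 8 mentions longitudinal modelling and multiple imputation. The first states no between-arm contrast and does not say how the therapy period is summarised. The others are not tied to the appetite endpoint.

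A reader might infer more than the documents support:

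- **That most of the information is discarded.** Among the step 2 ratios for 12 weeks, the variance saved exceeds half only at r = 0.3. For change from baseline under equal correlation it is 46%.
- **That subjects will lack a baseline VAS form.** Visits 0 and 1 are a week apart with ±7-day windows, so the gap can be short. But diaries start at Visit 0 and are collected at Visit 1. A missing form is possible, not shown.
- **That a missed last form leaves nothing current.** Section 8.3 allows a one-week look-back.
- **That appetite is the top-ranked secondary endpoint.** It is the named secondary aim, but the secondary endpoints are not ranked.

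**Conclusion.** The point holds in a limited form. The endpoint is a single end-of-therapy percent change with values carried forward, no between-arm analysis of the weekly VAS series is specified, and a substantial part of the collected information goes unused. For change from baseline under equal correlation, the variance is 0.625 (four-week mean) or 0.54 (12-week mean) of that for a single reading. These figures rest on an assumed correlation structure. Stronger correlation between adjacent weeks reduces the four-week gain, and a gradual effect can reverse the 12-week one. For the Week 12 contrast itself, the benefit comes from baseline adjustment and from not carrying early readings forward.

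Independently of any correlation, the instrument, the score and the scale (percent change or probability of suppression) are not settled. This should be corrected before analysis. It does not affect the primary endpoint.

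**What to change.** 1. State which instrument and which score define the appetite endpoint, and reconcile Sections 2.1, 6.1.3, 6.2 and 8.1.2. If it is the VAS, say which lines of the Appendix 5 form make up the score.
2. Keep the end-of-therapy between-arm contrast. Estimate it from a repeated-measures model of all on-therapy readings (weekly VAS; TFEQ at Weeks 1, 4, 8 and 12) with arm, week, arm-by-week, baseline score and site. Use the absolute score, without last value carried forward.
3. Report the Weeks 9-12 VAS mean from the same model as a supportive estimate.
4. Use all pre-randomisation VAS forms as the VAS baseline, and have every subject complete one form at Visit 1 before allocation is revealed. The trial is open label, so the order matters.

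The cost is SAP wording, a little more analysis work and one extra page at Visit 1. The model assumes data are missing at random, and the supportive mean smooths a change confined to the last week.

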#### Primary Effectiveness Endpoint:

The primary efficacy endpoint is the percent reduction in total body weight loss (%TBWL), measured as End Weight – Initial Weight divided by Initial Weight, multiplied by 100, at the end of Therapy period compared to Baseline between Treatment and Control.

Secondary Effectiveness Endpoints:

Number of subjects reporting >5% total body weight loss at the end of Therapy compared to Baseline between Treatment and Control

Percent change in appetite scores at the end of Therapy period compared to Baseline between Treatment and Control.

Blood pressure, blood lipids, CMP (Reduction in ALT) and HbA1c at the end of Therapy compared to Baseline between Treatment and Control groups.

% changes in BMI at the end of Therapy compared to Baseline between Treatment and Control groups

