## Statistical Analysis

Categorical variables will be summarized by number and percent. Continuous variables will be summarized by total number (N), mean, standard deviation (SD), median, minimum and maximum. Ninety-five percent, 2-sided confidence intervals on estimated means and differences in means between treatment and control groups will be calculated (corrected for multiplicity where needed). Confidence intervals will be similarly computed for proportions and differences between proportions. In addition, propensity score and sensitivity analyses will be utilized to compare adverse events and adverse device effects incidence versus historical control. Wilcoxon signed rank tests, Fisher exact tests, and Pearson Correlations will be utilized to compare changes in baseline variables between varying time points of the study (e.g. Baseline versus Therapy) and to correlate stimulation parameters with endpoint values.

Markov-chain Monte Carlo Analyses will be utilized to conduct Bayesian posterior probability distributions with multiple imputations allowed to assess treatment efficacy within and between cohorts. The need for additional endpoints to achieve primary and secondary significance will be determined utilizing longitudinal modeling. Finally, dose response will be modeled and analyzed within and between cohorts to determine optimal therapy dose for stimulation in open label period within and between cohorts using Normal dynamic linear modeling (NDLM) since monotonicity of the response cannot be assumed.

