### 8. STATISTICAL CONSIDERATIONS AND ANALYSIS PLAN

Categorical variables will be summarized by number and percent. Continuous variables will be summarized by total number (N), mean, standard deviation (SD), median, minimum and maximum. Ninety-five percent, 2-sided confidence intervals on estimated means and differences in means between treatment and control groups will be calculated. Confidence intervals will be similarly computed for proportions and differences between proportions. In addition, propensity score and sensitivity analyses will be utilized to compare adverse events and/or adverse device effects incidence versus historical control. Wilcoxon signed rank tests, Fisher exact tests, and Pearson Correlations will be utilized to compare changes in baseline variables between varying

time points of the study (e.g. baseline versus post stimulation treatment) and to correlate stimulation parameters with endpoint values. Markov-chain Monte Carlo Analyses will be utilized to conduct Bayesian posterior probability distributions with multiple imputations allowed to assess treatment efficacy within and between cohorts. The need for additional endpoints to achieve primary and secondary significance will be determined utilizing longitudinal modeling. Finally, dose response will be modeled and analyzed within and between cohorts to determine optimal therapy dose for stimulation in open label period within and between cohorts using Normal dynamic linear modeling (NDLM) since monotonicity of the response cannot be assumed.

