#### 8.1.3 Weight Loss

The null and alternative hypotheses are:

$$H_0$$
:  $π_T ≤ π_C$ 
 $H_1$ :  $π_T > π_C$ 

Where  $\pi_T$  and  $\pi_C$  are the probabilities of weight loss (% TBWL, %EBWL) in treatment versus control respectively. Estimates of the proportion of weight loss in pounds, % total body weight loss (%TBWL) Excess Body Weight Loss (%EBWL) or BMI will be compared with a tested Fishers Exact Test. Estimates and 95% confidence intervals will also be computed for the difference in rate of weight loss between varying stimulation levels.

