#### 8.2 JUSTIFICATION OF SAMPLE SIZE

The calculated sample size for the study is based on conservative imputation of results from other studies on weight loss including the use of TENS for weight loss. The degree of coaching/dietary support throughout the present study is moderate intensity lifestyle/weight coaching. The sample size modeling assumes an average of 3.5% TBWL in Control subjects using diet and exercise alone. The estimated weight loss in the Treatment subjects is modeled from preliminary data on T6/T7 dermatomal TENS when used for weight loss: 7.5% TBWL. The variance of the responses in the study (i.e. Standard Deviation) was modeled at + 5% TBWL. This value was taken from previous dermatomal TENS weight loss study results. The model assumes a 30% drop out rate across groups and an 80% powered endpoint using an adaptive p spending model wherein interim posterior probability assessments are allowed after enrolling proscribe cohorts of not less than 25 subjects per group for not less than 7 weeks of stimulation. The alpha penalty will be minimized per interim by assessing the relationship between stimulation (i.e. dose) and weight loss using Normalized Linear Dynamic Modeling (NLDM) to determine overall sample size projected (i.e. futility) rather than assessing the primary endpoint hypothesis per se. Monotonicity will not be assumed in this analysis. This modeling provides an estimate of 75 subjects per group, for a total study size of 150 subjects. However, the protocol allows for enrollment of additional subjects should the interim model project under powering of the primary endpoint.

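### Blood pressure, lipids, ALT and HbA1c get no analysis of their own and no baseline covariate; ANCOVA on baseline and site would recover precision at no cost

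*Combined protocol and SAP*

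**What the plan says.** Section 6.1.3 lists the endpoint as "Blood pressure, blood lipids, ALT and HbA1c at the end of Therapy Period as compared to Baseline between Treatment and Control groups". The Protocol Summary has nearly the same bullet: "Blood pressure, blood lipids, CMP (Reduction in ALT) and HbA1c at the end of Therapy compared to Baseline". Neither names a metric, although the bullet above it in Section 6.1.3 does: "Percent change in appetite scores at the end of Therapy Period compared to Baseline between Treatment and Control".

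Section 8 has analysis subsections for safety (8.1.1), appetite (8.1.2) and weight (8.1.3), and none for these four measures. Only its general text can apply to them. For estimation it says: "Ninety-five percent, 2-sided confidence intervals on estimated means and differences in means between treatment and control groups will be calculated". For testing, the Protocol Summary says "Wilcoxon signed rank tests, Fisher exact tests, and Pearson Correlations will be utilized to compare changes in baseline variables between varying time points", and Section 8 repeats the list. No test in that list is assigned to an endpoint.

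No baseline covariate, ANCOVA or adjusted mean appears anywhere. Propensity scores are reserved for adverse events against historical control. The Bayesian, longitudinal and dose-response models name no covariates.

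Section 5.3 blocks randomisation by site. Appendix 6 schedules blood tests at Visits 0 and 5, and blood pressure at every visit, so twice up to and including the randomisation visit (Visits 0 and 1).

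**The concern.** The endpoint is a contrast between arms, but the plan does not say how that contrast is formed. The signed rank test compares a subject with himself or herself. Kruskal-Wallis, which can compare groups, is named only under appetite in 8.1.2 and makes no use of baseline. That leaves an interval for a difference in means with nothing adjusted for.

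The trial is sized on weight alone (Section 8.2), so these endpoints have only the precision that the analysis gives them. Each measure has a baseline value that will probably explain much of the Week 12 variation. Leaving it out, or using it only by subtraction, gives a wider interval than the same data could support. Because the trial is open label, it also helps to fix beforehand whether change, percent change, end value or adjusted value will be reported.

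**Working it through.** **The plan's own figure.** The documents give no SD, power or sample size for these endpoints, so there is nothing to reproduce for them. The only sizing figure is 75 per group for percent weight loss. Section 8.2 takes 3.5% loss in Control ("The sample size modeling assumes an average of 3.5% TBWL in Control subjects using diet and exercise alone"), 7.5% in Treatment, SD 5%, 80% power and 30% dropout. A fixed two-sided 5% comparison of means gives 2 × (1.960 + 0.842)² × 5² / 4² = 24.5, so 25 per group, and 25/0.7 = 35.7, so 36 with dropout. That is not 75, but Section 8.2 attributes 75 to an adaptive model whose details are not given. Nothing below depends on it.

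**Inputs**
- From the plan: 75 per group and 30% dropout (Section 8.2), so 0.7 × 75 = 52.5, about 52 completers per arm.
- Assumed: correlation r between baseline and Week 12 of 0.3 to 0.9, and a common SD s at both times.

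**Formulas.** With n per arm, the contrast has variance 2V/n, where
- Week 12 value alone: V = s²
- raw change: V = 2s²(1−r)
- ANCOVA: V = s²(1−r²)

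Hence ANCOVA/change = (1−r)(1+r) / [2(1−r)] = (1+r)/2, and ANCOVA/Week 12 = 1−r². Both ratios are free of n. CI width scales with the square root of the ratio. The power column takes a contrast with 80% power on raw change and computes Φ(2.802/√ratio − 1.960).

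| r | Variance, ANCOVA/change | CI narrower by | Power if change has 80% | Variance, ANCOVA/Week 12 | CI narrower by |
|---|---|---|---|---|---|
| 0.3 | 0.65 | 19.4% | 93.5% | 0.91 | 4.6% |
| 0.5 | 0.75 | 13.4% | 89.9% | 0.75 | 13.4% |
| 0.7 | 0.85 | 7.8% | 86.0% | 0.51 | 28.6% |
| 0.9 | 0.95 | 2.5% | 82.0% | 0.19 | 56.4% |

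At r = 0.5, raw change is no better than ignoring baseline. ANCOVA with 75 per arm then matches change scores with 75/0.75 = 100 per arm.

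**Effect of carrying values forward.** Section 8.3 imputes by last value carried forward, and bloods are scheduled only at Visits 0 and 5. A dropout with no early-termination sample would therefore have an end value equal to baseline. If all 30% were like this, with equal variances and ignoring the shift in mean among completers, the pooled correlation is 0.7r + 0.3. For r = 0.3, 0.5, 0.7 and 0.9 that is 0.51, 0.65, 0.79 and 0.93. The variance saving over raw change, (1 − pooled r)/2, falls to 24.5%, 17.5%, 10.5% and 3.5%. This is the extreme case, since Appendix 6 asks for all end-of-study procedures at an early-termination visit. Blood pressure is less affected because it is taken at every visit.

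**The case against.** **The metric is not stated.** A reader might infer that the plan commits to raw change scores. The Protocol Summary does describe the HbA1c and ALT measures as changes, but the endpoint bullets name no metric and Section 8 does not say what the means are means of. The plan is silent on this, so the (1+r)/2 ratio applies only if change is what is meant. The conclusion does not need that reading: subtraction fixes the baseline coefficient at 1, ignoring baseline fixes it at 0, and ANCOVA estimates the coefficient that minimises variance.

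**Fisher's test.** A reader might also infer that Fisher's exact test will be applied to paired laboratory or blood pressure values. The documents do not say so. It stands in a generic list that also covers correlation with stimulation parameters, and it is tied to particular endpoints only in Section 8.1.3: "Excess Body Weight Loss (%EBWL) or BMI will be compared with a tested Fishers Exact Test". It would not be the cause of any precision loss here.

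**The gain may be small.** This stands. The documents give no r, one r is unlikely to suit four kinds of measure, and the HbA1c ceiling at entry (7.2.4) may make the SDs unequal. Against raw change the saving is 10% of variance at r = 0.8 and 5% at 0.9, and carrying baseline forward shrinks it further.

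**Randomisation already protects the comparison.** This also stands. An unadjusted contrast keeps its type I error, and its interval allows for chance imbalance at baseline. The case for adjustment is precision, not validity.

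**Visit 0 is already labelled baseline.** The visit name suggests that the Visit 0 reading is meant, and using it would be a legitimate choice. But blood pressure is measured again at Visit 1, and no text says which reading enters the analysis.

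**Conclusion.** The point holds as a gap in specification with a free improvement. For blood pressure, lipids, ALT and HbA1c, the plan offers a between-arm interval for means with no covariate and no stated metric. ANCOVA would be at least as precise asymptotically whichever metric was intended. Assuming equal SDs and r from 0.3 to 0.9, the variance saving is 35% down to 5% against raw change (24.5% down to 3.5% for laboratory values in the extreme carry-forward case), and 9% up to 81% against the Week 12 value alone. The direction follows from the algebra; the size rests on a correlation that the documents do not supply.

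The point concerns these four measures only, since the responder, appetite and BMI endpoints are defined differently. It does not show that the unadjusted analysis is invalid, and it does not bear on the primary endpoint.

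**What to change.** Add a subsection to Section 8 stating that each of these endpoints is analysed by ANCOVA: the Week 12 value regressed on arm, that measure's own baseline value and site, reporting the adjusted arm difference with its two-sided 95% CI. The site term matches the blocking in Section 5.3. State in the same place which pre-randomisation blood pressure reading, Visit 0 or Visit 1 or a stated combination, is baseline.

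The cost is wording only, because every value needed is already scheduled in Appendix 6. With up to 10 centres the model uses at most 9 degrees of freedom for site and 1 for baseline. With about 104 completers that leaves 104 − 1 − 1 − 1 − 9 = 92 residual degrees of freedom after the intercept and arm, so the finite-sample price is small. Averaging the two blood pressure readings or analysing ALT on a log scale are reasonable options, but the documents give no grounds for requiring either.
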